4.4.3 Study Endpoints

The primary safety endpoint is freedom from major adverse events (MAE) at 30 days or during hospitalization if this exceeds 30 days.

Major adverse events include death, bowel ischemia, myocardial infarction, paraplegia, renal failure, respiratory failure, and stroke.

The primary effectiveness endpoint is the proportion of the study subjects with treatment success at 1 year. Treatment success is defined as a composite of technical success and freedom from the following:

- Aneurysm enlargement i.e., $\geq 5\text{mm}$ as compared to any previous CT measure using orthogonal (i.e., perpendicular to the centerline) measurements
- Aneurysm rupture
- Aneurysm-related mortality
- Conversion to open repair
- Secondary intervention for migration, Type I and III endoleaks, device integrity failure (e.g., fracture), and patency-related events (i.e., device component stenosis or occlusion and embolic events)

Secondary endpoints include:

- Technical success and the individual components of technical success:
 - Successful delivery
 - Deployment at the intended implantation site
 - Patency of all endovascular graft and stent components
 - Absence of device deformations requiring unplanned placement of an additional device
 - Absence of inadvertent covering of aortic branch vessels
 - Successful withdrawal
- Freedom from the individual components of the primary safety endpoint at 30 days:
 - Death
 - Bowel ischemia
 - Myocardial infarction
 - Paraplegia
 - Renal failure
 - Respiratory failure
 - Stroke
- Freedom from paraparesis at 30 days
- The following at each follow-up interval:
 - Treatment success and the individual components of treatment success including freedom from the following:
 - Aneurysm enlargement
 - Aneurysm-related mortality

- Aneurysm rupture
- Conversion to open repair
- Secondary intervention for migration, type I and III endoleaks, device integrity failure (i.e., fracture), and patency-related events (i.e., device stenosis or occlusion and embolic events).
- Renal failure
- All-cause mortality
- Endoleaks
- Device integrity failure (e.g., fracture)
- Patency-related events (i.e., device stenosis or occlusion and embolic events)
- Other device-related events

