4.4.5 Patient Enrollment and Screening

The investigator will assess potential study subjects with thoracoabdominal aortic aneurysms for their suitability for enrollment into the clinical study. If the patient appears to meet eligibility criteria, either for the primary study arm or the expanded selection arm, then the investigator or clinical study coordinator will discuss the study with the patient and provide patient education materials to adequately inform the patient of potential risks and benefits, required follow-up procedures, and answer any questions. The clinical study coordinator will facilitate the informed consent process. After the patient has been properly consented, the patient will complete additional screening procedures that need to be completed. If the patient does not sign the informed consent, they will not be enrolled in the study. Information to be collected for screening includes:

- Patient demographics
- Medical history
- Current health status
- Physical examination
- Ankle Brachial Index (ABI)
- Pregnancy test (for female patients of childbearing age)

- An X-Ray will be performed per local standard of care. A/P, Lateral and Bilateral Oblique Images will be obtained.
- CTA of the chest, abdomen, and pelvis with 3D reconstruction if renal function allows to evaluate:
 - Access vessels for compatibility with vascular access techniques
 - Obstructive stenting of the visceral vessels
 - Vessel diameters suitable for use with the Valiant™ Thoracoabdominal Stent Graft System
 - Aneurysm rupture
 - Branch stenosis
 - Dissection
 - Patency of left subclavian artery, hypogastric arteries, lumbar arteries, and all four visceral vessels
 - Thrombus or excessive calcification in the neck of the aneurysm
 -
- Complete blood count
- Basic metabolic panel
- For patients with a history of smoking a pulmonary function test
- Cardiac clearance

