4.4.5.3 Implant Procedures

Note I: For proximal extension of the thoracic bifurcation, two Valiant Captivia or Valiant Navion thoracic grafts can be used. One to extend the landing zone more proximally and one to layer to prevent wear. Deploy the Valiant Captivia or Valiant Navion thoracic grafts according to their respective manufacturer's IFU and continue according to the implant procedures the Medtronic Valiant Thoracoabdominal Stent Graft System IFU.

Note II: For subjects with advanced iliac atherosclerosis and calcification, we will selectively perform use of open conduits to deliver devices, rather than percutaneous approach. We will selectively perform on table Dyna CT – angiograms at the completion of the case. This will give us a better 3-Dimensional image of the stent and help determine if there is any degree of compression, which can be treated at that time with further stenting.

A. The use of thoracic grafts as a method of staging as a pre-operative adjunct procedure.

a. Thoracic Graft Placement

i. This refers to implanting stent-grafts into the thoracic aorta prior to enrollment into the IDE clinical study.

ii. Device Visualization and Preparation

Refer to the Instructions for use provided for the thoracic components to be used.

iii. Device Placement

Ensure that the distal edge of the thoracic graft is 5-7 cm proximal to the celiac artery.

iv. Thoracic Aorta Component Deployment

Follow the study protocol or IFU for deploying the thoracic graft components.

v. Completion

The date of the index procedure will be targeted for within 6 weeks of the thoracic graft placement, but will be based on physician discretion, clinical presentation, and patient compliance.

B. The implantation of the Valiant™ Thoracoabdominal Stent Graft System is conducted under fluoroscopic/angiographic guidance. Refer to the Valiant™ Thoracoabdominal Stent Graft System (IFU) for techniques and methods for device deployment and implantation.

C. The Valiant Thoracoabdominal Stent Graft System may be implanted in a staged procedure per physician discretion (in either a planned or bail-out fashion). The physician may choose to perform the procedure in two or more stages due to the following conditions/scenarios including but not limited to: hypogastric patency, LSA patency, visceral vessel patency, decreased MEP/SEP potentials, at risk dominant segmental arteries, pulmonary status, or any patient whose

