Additionally, the sponsor will send an Interim Report for every five patients regardless of study arm, and within the report divide those 5 into their respective primary or expanded selection cohorts.

These reports will include basic information on the number of patients enrolled and treated and information on observed adverse events for any subgroups (e.g., device types, extents of disease, lesion types). These interim progress reports are meant to be summaries and not complete progress reports. Details will be captured in any adverse event reports and annual reports to the IDE.

Table 9: Enrollment summary*

	column for each subgroup	Total
Enrolled		
Treated		
Awaiting treatment		
Withdrawn (state reason)		

* A subject is considered enrolled after the device enters the body.

Summary

For each subgroup of patients, a brief narrative description of the procedures completed to date (e.g., how many had devices implanted successfully), any need for additional interventions, and the outcomes of any additional interventions will be provided.

Table 10: Treatment summary

	Number of patients	Procedural success	Perioperative death
One branch			
Two branches			
Three branches			
Four branches			
Total			

Adverse Events

Comments on the most commonly observed challenges or adverse events will be provided.

The following table is an example of how adverse event numbers may be presented for each subgroup. The list will include events observed in the study, not necessarily all that are listed in this example	1 st 5	2 nd 5	Additional groups	All
Aortic dissection				
Branch vessel embolism (renal, celiac, SMA, etc.)				
Branch vessel occlusion (renal, celiac, SMA, etc.)				
Branch vessel dissection (renal, celiac, SMA, etc.)				
External iliac dissection				
Interval iliac occlusion				
Ischemic colitis/Colon necrosis				
Late related death				
Late unrelated death				
Leg ischemia				
Lower extremity embolism				
Lower extremity paralysis				
MI				
Perioperative death				
Renal failure/impairment				
Respiratory failure				
Stroke				
Wound necrosis				

Table 6: Adverse Events

Study subjects who had multiple complications will be designated using symbols (#, *, +) or numbers.

Lessons Learned

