Type Ic: leak occurring at the distal fixation zone of the covered stents in the visceral vessels incorporated by the fenestrations

Type II: leak caused by retrograde flow from patent lumbar or inferior mesenteric arteries

Type IIIa: leak caused by a defect in the graft fabric

Type IIIb: leak caused by inadequate seal between modular graft components

Type IV: leak caused by graft fabric porosity, often resulting in a generalized blush of contrast within the aneurysm sac .

Endoleak, Early: any endoleak observed within 30 days after device deployment

Endoleak, Late: any endoleak observed later than 30 days after deployment that was not documented during the first 30 days after deployment

Estimated Glomerular Filtration Rate (eGFR): estimated GFR (mL/min/1.73 m²) = 175 x (Serum creatinine)-1.154 x (Age)-0.203x (0.743 if female) x (1.210 if African-American)

Limb occlusion: the presence of thrombus within any graft limb that creates occlusion

Major adverse events: all-cause mortality, bowel ischemia (requiring medical or surgical management), myocardial infarction, paraplegia, renal failure, respiratory failure, and stroke

- **All-Cause Mortality:** any death occurring within the first 30 days post procedure
- **Bowel Ischemia:** Bowel ischemia due to limb or arterial occlusion, graft placement, or embolization.
- **Myocardial infarction:** raised levels of cardiac biomarkers or ECG changes
- **Paraplegia:** spinal cord ischemic event resulting in complete loss of motor function with or without loss of sensation in the lower extremities

- **Renal Failure:** acute or progressive renal insufficiency leading to the need for dialysis or hemofiltration
- **Respiratory failure:** Prolonged intubation (>48 hours after spinal drain removal or >72 hours total) and/or reintubation. This definition does not put the patient at any increased risk. The high risk patient population being treated in this study is prone to pre-existing comorbidities, including COPD and decreased respiratory function, and may require extended ventilator support while in the supine position for spinal drainage.
- **Stroke:** neurological deficit that lasts > 24 hours

Malperfusion of organ(s) or limb(s): loss of flow through a particular vascular bed has been partially or completely compromised leaving the said organ or limb ischemic

Migration, clinically significant: antegrade or retrograde migration that requires surgical or endovascular intervention

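### Thoracic graft staging is placed before enrolment, so deaths and paraplegia at that stage or during the wait fall outside the primary safety endpoint

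*Combined protocol and SAP*

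**What the plan says.** Part A of section 4.4.5.3 (Implant Procedures) introduces "The use of thoracic grafts as a method of staging as a pre-operative adjunct procedure". It gives a landing position relative to the celiac artery and refers the operator to the protocol or the instructions for use. On timing it says "This refers to implanting stent-grafts into the thoracic aorta prior to enrollment into the IDE clinical study". It adds: "The date of the index procedure will be targeted for within 6 weeks of the thoracic graft placement". The actual date is left to physician discretion, clinical presentation and patient compliance, and no maximum is given.

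Enrolment is defined only in the footnote to Table 9 (section 4.7): "A subject is considered enrolled after the device enters the body". Section 4.4.5 makes consent a condition, "If the patient does not sign the informed consent, they will not be enrolled in the study", but gives no time point.

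Section 4.4.3 states: "The primary safety endpoint is freedom from major adverse events (MAE) at 30 days or during hospitalization if this exceeds 30 days". It continues: "Major adverse events include death, bowel ischemia, myocardial infarction, paraplegia, renal failure, respiratory failure, and stroke". It names no time zero. Section 4.9 limits the death component to "any death occurring within the first 30 days post procedure" and ties the first limb of aneurysm-related mortality to the index procedure.

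Section 4.4.7.1 tests the 30-day MAE rate against a 50% performance goal built from open-repair literature. The test is exact, one-sided at 2.5%, with 46 subjects pooled across physician-sponsored IDEs and an anticipated rate of 26%.

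**The concern.** The thoracic graft in part A is not incidental history. The protocol describes it as a stage of the planned repair and sets a target interval to the next operation. If that stage lies before enrolment and the endpoint is counted from the later operation, only patients who get through the first stage and the wait can enter the study. The endpoint would then describe survivors of the pathway, and what happened to the others would not be recorded anywhere.

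At stake are all seven MAE components. Rupture and aneurysm-related death, which feed the one-year treatment success composite, are affected too. Section 3.4.2.1 lists paraplegia, spinal cord ischemia, rupture and death among the added risks of staging, although it was written for the two methods that begin with the study device. The six staged cases in section 3.5.1 also used those two methods. The documents therefore hold no safety data on thoracic graft staging with this system, and the plan as written would collect none for the interval.

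**Working it through.** **Step 1. Follow a patient through the rules.**

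- *Dies, or ruptures and is never implanted, between the two operations.* The device never enters the body, so by the Table 9 footnote the patient is not enrolled and is absent from numerator and denominator.
- *Paralysed at the thoracic stage, then returns.* The patient is enrolled and in the denominator, but the event came before the index procedure. Section 4.4.3 does not state a time zero, so its exclusion is inferred. It is the natural reading, because section 4.4.5.3 uses the term index procedure for the later operation and section 4.9 counts procedural death from it.
- *Is there a route back in?* I found none. Follow-up accounting in Table 8 starts at the operative row. Scheduled safety board meetings during enrolment (section 4.8) are triggered by primary-arm patients receiving the investigational device.

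**Step 2. Primary arm, six patients, no counted events.**

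- One omitted death: 1/7 = 14.3% on the whole pathway, reported as 0/6 = 0%.
- One omitted paraplegia in a patient who returns: 1/6 = 16.7%, reported as 0/6 = 0%.

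**Step 3. Reproduce the plan's own figure.** Take X ~ Binomial(46, 0.50) under the goal. The largest count with P(X ≤ c) ≤ 0.025 is c = 15, with exact size 0.0129. At a true rate of 26%, P(X ≤ 15) = 0.881. The plan's claim of at least 80% power is therefore correct as an inequality.

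**Step 4. Pooled test at its boundary.** Exact lower-tail p-values against 50%:

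| Events restored | Count | p | Result |
|---|---|---|---|
| none | 15/46 | 0.013 | passes |
| one death | 16/47 | 0.020 | passes |
| two deaths | 17/48 | 0.030 | fails |
| one paraplegia, patient returned | 16/46 | 0.027 | fails |

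**Step 5. Range of possible bias.** Let f be the share of patients staged this way and q the probability of an MAE at the thoracic stage or in the wait. Neither is in the documents; I assume f = 10% to 100% and q = 3% to 15%. With 26% kept for the index procedure:

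- whole-pathway rate = fq + (1 − fq) × 0.26
- understatement = fq × (1 − 0.26)
- if the whole-pathway rate is really 50%, the index-only rate is (0.5 − fq)/(1 − fq)

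For example, f = 50% and q = 10% gives 0.05 + 0.95 × 0.26 = 29.7%, and 0.45/0.95 = 47.4% for the index-only rate under the null.

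| f | q | Whole-pathway rate | Power at 46, counted from first stage | Type I error, index-only test |
|---|---|---|---|---|
| 10% | 3% | 26.2% | 87.4% | 0.014 |
| 50% | 5% | 27.9% | 81.3% | 0.020 |
| 50% | 10% | 29.7% | 72.8% | 0.031 |
| 100% | 10% | 33.4% | 52.4% | 0.070 |
| 100% | 15% | 37.1% | 32.0% | 0.151 |

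The understatement runs from 0.2 points (0.003 × 0.74) to 11.1 points (0.15 × 0.74). Type I error exceeds 2.5% only in the last three rows.

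**The case against.** The best defence is that counting from the index procedure is a legitimate choice. Section 4.1 aims at the safety of this device, section 4.4.2 accepts previously placed graft material in the landing zone, and section 4.4.5.3 calls the thoracic graft an adjunct. This stands as a reason to keep the index-procedure rate. It does not explain why patients who start a protocol-described stage and never reach the device should go unreported.

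The route may also be rare. Section 4.4.5.3 names a controlled endoleak as the preferred method of planned staging. That method starts with the study device and so does not have this gap. This stands too, and it is why no size can be attached.

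Four stronger readings are tempting, but the documents do not support them.

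- *The 11% (3/27) spinal cord ischemia rate in section 3.3.3.8.1 measures the uncounted risk.* It covers the whole two-stage repair and is not split by stage. All three events resolved by discharge, and single-stage repair in the same series had 37.5% (12/32). The MAE component is complete loss of motor function; paraparesis is a separate secondary endpoint.
- *The open-repair goal counts the whole repair, so the comparison is unequal.* Table 6 gives event counts only and does not show how the cited series handled earlier stages.
- *The uncounted period lasts at most six weeks.* Six weeks is a target without a maximum.
- *The protocol states that the 30-day clock starts at device entry.* The footnote defines enrolment, not the MAE window. It also sits badly with the table's own row for subjects awaiting treatment. The clock is inferred.

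**Conclusion.** The gap is real and follows from rules the plan states: the thoracic stage lies before enrolment, enrolment is at device entry, and nothing brings interval events back. Every event left out lowers the reported MAE rate, so the bias from these omissions runs only in the device's favour.

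Its size is unknown. The calculations show what would follow under assumed values of f and q, and how few events matter in a six-patient arm or at the pooled boundary. They do not show that the study's result will be materially wrong; at 10% use and a 3% event rate the understatement is 0.2 points. The pooled figures also assume that these omissions could arise anywhere among the 46. If only this site staged in this way, f would be at most about 15/46 = 33%, or 6/46 = 13% if only its primary arm enters the pool.

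The conclusion rests on reading the 30-day window as starting at the index procedure. The loss of patients who are never implanted does not depend on that reading.

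**What to change.** Where a thoracic graft is placed as a planned stage for this system:

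- obtain consent and register the patient before that stage;
- record MAEs, rupture and death from that stage onward;
- report every pre-staged patient, including those who never reach the index procedure;
- present the MAE rate counted from the first stage beside the index-procedure rate, and state the time zero of each in section 4.4.3.

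The cost is earlier consent, a short log for a study of 15 patients, and a possibly less favourable MAE rate. Clinical care and the timing of the operations do not change.

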4.4.5.4 Completion Procedures

1. At the physician's discretion line the bridging stent grafts with self-expanding bare metal stent(s) to provide additional radial support. *Note: In the event a bridging stent or self-expanding stent needs reinforcement a Viabahn stent graft of appropriate sizing may be used.*
2. Begin to optimize spinal perfusion.
3. After deployment of all stent grafts, all contact points will be balloon angioplasties.
4. Perform an angiogram to verify stent graft apposition, seals, patency, device defects and any endoleaks. Perform additional procedures, such as ballooning, cuff placement, or use of covered stent grafts as necessary to treat endoleaks or device failures. Perform any adjunct procedures including but not limited to ballooning, atherectomy, or placement of stents to repair or treat any arterial issues or concomitant disease process in the iliac system to maintain flow to the lower extremities or the upper access arm extremity.
5. Remove all sheaths, wires, and remaining accessories and repair of arterial access sites using standard surgical closure techniques.
6. Dopplerable signals will be confirmed in bilateral lower extremities and the access upper extremities.

7. Once adequate perfusion is confirmed, heparinization will be reversed.
8. In the event of patient death an autopsy may be performed.

4.4.5.5 Post-operative Care

Patients may remain intubated and be transferred to the ICU standard post-operative care. Patients with a spinal drain will remain in bed with optimization of spinal perfusion pressure for 48-72 hours whenever possible. Post-operative care will be tailored to the patient taking into account events of surgery as well as pre-operative comorbidities to optimize the patient's recovery. On post-operative day two, attempts will be made to normalize the MAP and clamp the spinal drain if used. Prior to spinal drain removal all coagulopathies and low platelet counts are corrected. The patient's neurological status is closely watched for the next 4-6 hours. If it remains stable, the drain is removed and the patient is monitored for hypoxia, anemia, and hypotension. In the event of patient death an autopsy may be performed. Prior to discharge from the hospital, the following tests will be performed:

- Physical examination
- Complete blood count to evaluate white blood cells, hemoglobin, and platelets
- Basic metabolic panel to evaluate creatinine
- Prothrombin time (at physician's discretion)
- Partial thromboplastin time (at physician's discretion)
- CTA of the chest, abdomen, and pelvis if clinically necessary and renal function allows

4.4.5.6 Follow-up Visits

All patients will undergo follow-up at one month, six months, twelve months and then annually for five years (as described in Section 1.4.4). At each of the follow-up visits the following tests will be performed:

- Physical examination
- Complete blood count to evaluate white blood cells, hemoglobin, and platelets
- Basic metabolic panel to evaluate creatinine
- Pregnancy test (for female patients of child bearing age)
- CTA of the chest, abdomen, and pelvis if renal function allows
- If deemed necessary by the investigator, an X-Ray may be performed if potential device integrity issues are identified but unable to be confirmed by CT. This will be done per local standard of care with A/P, Lateral and Bilateral Oblique Images obtained.

4.4.6 Sample Size Justification

The sample size for the feasibility study is limited to 15 patients, as this is adequate to provide preliminary clinical safety data and effectiveness of the device. We plan for 6 subjects to enroll in the primary arm, and 9 subjects to be enrolled under extended criteria. The device, while novel, has been evaluated in a clinical setting and has initially demonstrated both safety and effectiveness. The limited sample size allows adequate patient data to be collected under a controlled protocol without exposing a large patient population to the risk associated with a novel device design. The safety and effectiveness data collected in this study will be pooled with other physician sponsored investigational device exemptions (PS-IDEs) evaluating the Visceral Manifold System and should be sufficient to develop an appropriate pivotal study.

